#### Events Meeting the AE Definition

- Any abnormal laboratory test results (hematology, clinical chemistry, or urinalysis) or other safety assessments (for example, electrocardiogram, radiological scans, vital signs measurements), including those that worsen from baseline, considered clinically significant in the medical and scientific judgment of the investigator (that is, not related to progression of underlying disease).
- Exacerbation of a chronic or intermittent preexisting condition, including either an increase in frequency and/or intensity of the condition.
- New conditions detected or diagnosed after study intervention administration, even though they may have been present before the start of the study.
- Signs, symptoms, or the clinical sequelae of a suspected drug-drug interaction.
- Signs, symptoms, or the clinical sequelae of a suspected overdose of either study intervention or a concomitant medication. Overdose per se will not be reported as an AE/SAE, unless it is an intentional overdose taken with possible suicidal/self-harming intent. Such overdose should be reported regardless of sequelae.
- The signs, symptoms, and/or clinical sequelae resulting from lack of efficacy will be reported as AEs or SAEs if they fulfill the definition of an AE or SAE. Also, 'lack of efficacy' or 'failure of expected pharmacological action' also constitutes an AE or SAE.

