### 9.2. Sample Size Determination

Approximately 280 participants will be randomized at a 3:2:2 ratio to lebrikizumab 250 mg Q2W, lebrikizumab 250 mg Q4W, or placebo (120 participants: 80 participants: 80 participants). The inclusion of approximately 15 adolescents is based on enrollment feasibility in Japan.

The assumed IGA score of 0 or 1 at Week 16 response rates are 38% for lebrikizumab 250 mg Q2W, 33% for lebrikizumab 250 mg Q4W, and 13% for placebo. The assumed EASI-75 response rates at Week 16 are 58% for lebrikizumab 250 mg Q2W, 53% for lebrikizumab 250 mg Q4W, and 20% for placebo. The assumptions for lebrikizumab are based on the DRM06-AD01 Phase 2b study, and the proportion of participants who achieved an IGA score of 0 or 1 and proportion of participants who achieved EASI-75 response at Week 16 using the rescue medication nonresponse sensitivity analysis, adjusting for the allowed use of TCS. The placebo response rate is based on the review of historical TCS clinical studies in AD (Simpson et al. 2016). This study has  $>95\%$  and  $>80\%$  power to test the superiority of lebrikizumab 250 mg Q2W to placebo and lebrikizumab 250 mg Q4W to placebo in the co-primary endpoints based on a two-sided Fisher exact test with alpha of 0.05.

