**Events NOT Meeting the AE Definition**

- Any clinically significant abnormal laboratory findings or other abnormal safety assessments which are associated with the underlying disease, unless judged by the investigator to be more severe than expected for the participant's condition.
- The disease/disorder being studied or expected progression, signs, or symptoms of the disease/disorder being studied, unless more severe than expected for the participant's condition.
- Medical or surgical procedure (for example, endoscopy, appendectomy): the condition that leads to the procedure is the AE.
- Situations in which an untoward medical occurrence did not occur (social and/or convenience admission to a hospital).
- Anticipated day-to-day fluctuations of preexisting disease(s) or condition(s) present or detected at the start of the study that do not worsen.

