**10.3.2. Definition of SAE**

If an event is not an AE per definition above, then it cannot be an SAE even if serious conditions are met (for example, hospitalization for signs/symptoms of the disease under study, death due to progression of disease).

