Listing of AE (including AEs in the Maintenance Period and the Follow-Up Period)	S

Abbreviations: A = All Lebrikizumab Safety Population; AE = adverse event; ITT = Intent-to-Treat; MPP = Maintenance Primary Population; MSP = Maintenance Secondary Population; PT = Preferred Term; SAE = serious adverse event; S = Safety Population; SOC = System Organ Class; TEAE = treatment-emergent adverse event.

Statistical comparisons will be performed for Safety Population using Fisher's exact test. OR will be provided.

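### Protocol Appendix 3 makes lack of efficacy an AE or SAE without condition, against its own neighbouring rules, and literal use could inflate aggregate Induction Period TEAE incidence on placebo

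*Protocol*

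**What the plan says.** Four statements in the Protocol bear on this.

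- Appendix 3, Events Meeting the AE Definition, last bullet, first sentence: signs, symptoms or sequelae "resulting from lack of efficacy will be reported as AEs or SAEs if they fulfill the definition of an AE or SAE". This is conditional.
- Same bullet, next sentence: "Also, 'lack of efficacy' or 'failure of expected pharmacological action' also constitutes an AE or SAE". This is unconditional.
- Appendix 3, Events NOT Meeting the AE Definition, lists "The disease/disorder being studied or expected progression, signs, or symptoms of the disease/disorder being studied, unless more severe than expected" for the participant's condition.
- Section 10.3.2: "If an event is not an AE per definition above, then it cannot be an SAE even if serious conditions are met", and one of its two examples is "hospitalization for signs/symptoms of the disease under study".

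The SAP (4.6.2) defines a TEAE as an event that first occurs or worsens after baseline, with no exclusion for lack-of-efficacy terms. For AEs it then states: "Statistical comparisons will be performed for Safety Population using Fisher's exact test".

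**The concern.** A participant whose atopic dermatitis persists, no worse than expected, is an AE case under one sentence and not under the others. Sites that read Appendix 3 differently will record the same clinical course differently.

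The ambiguity is not neutral between arms. Lack of efficacy should be more common on placebo, and sites know who has failed: they score IGA and EASI, record rescue treatment, and move Week 16 non-responders to the Escape Arm. If some of them follow the unconditional sentence, the added AEs fall mainly on placebo. Overall TEAE incidence would then rise more there than on lebrikizumab, and a true excess on lebrikizumab could be narrowed in the aggregate rows. An AE entry adds little, because the failure is already captured in the efficacy and rescue data.

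**Working it through.** **Inputs from the documents.** Protocol 9.2 gives "assumed EASI-75 response rates at Week 16 are 58% for lebrikizumab 250 mg Q2W, 53% for lebrikizumab 250 mg Q4W, and 20% for placebo", and IGA 0/1 rates of "38% for lebrikizumab 250 mg Q2W, 33% for lebrikizumab 250 mg Q4W, and 13% for placebo". Arm sizes are 120, 80 and 80.

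**Check that the planning rates are read correctly.** Exact power of the two-sided Fisher test at alpha 0.05:

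- Q2W vs placebo: 97.9% for IGA 0/1 and 99.98% for EASI-75, so 97.9% for both if independent.
- Q4W vs placebo: 82.5% and 99.1%, so 81.8% for both if independent.

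These agree with the stated >95% and >80%.

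**Planned non-response** = 1 − response rate.

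| | Placebo | Q2W | Q4W |
|---|---|---|---|
| EASI-75 | 80% | 42% | 47% |
| IGA 0/1 | 87% | 62% | 67% |

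The placebo-minus-Q2W difference is 38 points on EASI-75 and 25 points on IGA 0/1. These rates are upper bounds for the affected pool, for the reason given under the objection.

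**Assumptions not in the documents.** Let b be the true TEAE rate, equal in all arms and independent of response. Let f be the fraction of non-responders also recorded as an AE. With NR for non-response:

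observed incidence = 1 − (1 − b)(1 − f × NR)

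spurious gap = (1 − b) × f × (NR placebo − NR lebrikizumab)

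**Results at b = 50%, Q2W vs placebo.** For example, at f = 50% on EASI-75: placebo 1 − 0.5 × (1 − 0.40) = 70.0%; Q2W 1 − 0.5 × (1 − 0.21) = 60.5%; gap 9.5 points.

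| f | Placebo (EASI-75) | Q2W (EASI-75) | Gap, EASI-75 | Gap, IGA 0/1 | Chance Fisher flags a difference (EASI-75) |
|---|---|---|---|---|---|
| 0 | 50.0% | 50.0% | 0 | 0 | 4.2% |
| 10% | 54.0% | 52.1% | 1.9 | 1.25 | 5.0% |
| 25% | 60.0% | 55.25% | 4.75 | 3.1 | 9.1% |
| 50% | 70.0% | 60.5% | 9.5 | 6.25 | 25.5% |
| 100% | 90.0% | 71.0% | 19.0 | 12.5 | 91.0% |

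For Q4W on EASI-75 the gap is 0.5 × f × 33 points: 8.25 at f = 50% and 16.5 at f = 100%.

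**Sensitivity to b (Q2W, EASI-75).** At f = 10% the gap is 2.7, 1.9 and 1.1 points for b = 30%, 50% and 70%. At f = 100% it is 26.6, 19.0 and 11.4.

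**The case against.** The best counter-argument is that the text supports much less than a biased safety comparison. Most of it stands.

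- **Who is affected.** A reader might infer that every non-responder becomes an AE. Neither document equates missing EASI-75 with lack of efficacy. Response is a Week 16 threshold, whereas lack of efficacy appears as a reason for stopping. A participant with a 60% EASI improvement is a non-responder without being an evident drug failure, and an AE must still be an untoward medical occurrence. The 80% and 42% are therefore a ceiling.
- **Timing.** Non-response is established at the Week 16 visit. SAP 4.1.1 ends the Induction Period before the first Week 16 injection, and 4.6.1 dates its last visit to the day before the first Maintenance visit. Some such events may fall outside the Induction tables.
- **SAEs.** A reader might infer that non-response becomes an SAE. The SAE definition still requires a seriousness criterion, which non-response alone does not meet.
- **Masking.** AEs are also tabulated by preferred term, so a lack-of-efficacy term would be a visible row. Conjunctivitis, infections, injection site reactions and atopic dermatitis exacerbation have their own tables. SAP 4.6 treats safety p-values as flags only. The Maintenance Primary Population has no between-group comparison, and the All Lebrikizumab set has no comparator.
- **Efficacy.** A reader might infer that the ambiguity reaches the co-primary analysis, because the primary estimand handles discontinuation for lack of efficacy differently from other reasons. Nothing in the documents says that recording lack of efficacy as an AE would change the discontinuation reason. That remains a possibility and is not counted here.

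These points limit the size and reach. They leave the contradiction in place, and no SAP rule takes such events out of the overall TEAE count.

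**Conclusion.** The point holds as a moderate wording error in current text; it is not a flaw of design. The unconditional sentence conflicts with the sentence before it, with the list of non-events and with 10.3.2. Followed literally, it adds AEs mainly to placebo in the only between-arm AE comparison. The exposure is mainly the aggregate TEAE rows of the Induction Period Safety Population.

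The documents support saying that this comparison could be tilted towards lebrikizumab, not that it is. The size depends on a reporting fraction and a true TEAE rate that neither document gives. At 10% reporting the artefact is about 1 to 3 points and the false-flag rate barely moves. It becomes large only if half or more of non-responders are recorded, and the 19-point figure requires all of them. On IGA 0/1 the corresponding gaps are smaller, about 6 points at half and 12.5 at full reporting.

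**What to change.** 1. **Protocol Appendix 3.** Reconcile the last bullet of the qualifying events with the list of non-events and with 10.3.2. For example, remove the unconditional sentence, or put it under the same condition as the sentence before it. The result should be that lack of efficacy alone is captured by the efficacy assessments and rescue records, and only signs, symptoms or sequelae that meet the AE definition are reported, subject to any local reporting requirement. The same list already treats overdose this way: overdose alone is not an AE unless self-harm may have been intended.
2. **Sites.** Send a short clarification so that all sites apply one rule.
3. **SAP 4.6.2.** Present overall TEAE incidence with any lack-of-efficacy terms already recorded shown separately, so that the aggregate comparison can be read without them.

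The cost is one sentence in the protocol, one site notice and one extra line in the TEAE overview. No additional data or participants are needed.

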**Events NOT Meeting the AE Definition**

- Any clinically significant abnormal laboratory findings or other abnormal safety assessments which are associated with the underlying disease, unless judged by the investigator to be more severe than expected for the participant's condition.
- The disease/disorder being studied or expected progression, signs, or symptoms of the disease/disorder being studied, unless more severe than expected for the participant's condition.
- Medical or surgical procedure (for example, endoscopy, appendectomy): the condition that leads to the procedure is the AE.
- Situations in which an untoward medical occurrence did not occur (social and/or convenience admission to a hospital).
- Anticipated day-to-day fluctuations of preexisting disease(s) or condition(s) present or detected at the start of the study that do not worsen.

**10.3.2. Definition of SAE**

If an event is not an AE per definition above, then it cannot be an SAE even if serious conditions are met (for example, hospitalization for signs/symptoms of the disease under study, death due to progression of disease).

**An SAE is defined as any untoward medical occurrence that, at any dose:****a. Results in death****b. Is life-threatening**

The term 'life-threatening' in the definition of 'serious' refers to an event in which the participant was at risk of death at the time of the event. It does not refer to an event which hypothetically might have caused death if it were more severe.

**c. Requires inpatient hospitalization or prolongation of existing hospitalization**

- In general, hospitalization signifies that the participant has been admitted to hospital for observation and/or treatment that would not have been appropriate in the physician's office or outpatient setting. Complications that occur during hospitalization are AEs. If a complication prolongs hospitalization or fulfills any other serious criteria, the event is serious. When in doubt as to whether 'hospitalization' occurred or was necessary, the AE should be considered serious.
- Hospitalization for elective treatment of a preexisting condition that did not worsen from baseline is not considered an AE.

**d. Results in persistent disability/incapacity**

- The term disability means a substantial disruption of a person's ability to conduct normal life functions.

- This definition is not intended to include experiences of relatively minor medical significance such as uncomplicated headache, nausea, vomiting, diarrhea, influenza, and accidental trauma (for example, sprained ankle) which may interfere with or prevent everyday life functions but do not constitute a substantial disruption.

**e. Is a congenital anomaly/birth defect****f. Other situations:**

- Medical or scientific judgment should be exercised in deciding whether SAE reporting is appropriate in other situations such as important medical events that may not be immediately life-threatening or result in death or hospitalization but may jeopardize the participant or may require medical or surgical intervention to prevent one of the other outcomes listed in the above definition. These events should usually be considered serious.
- Examples of such events include invasive or malignant cancers, intensive treatment in an emergency room or at home for allergic bronchospasm, blood dyscrasias or convulsions that do not result in hospitalization, or development of drug dependency or drug abuse.

**10.3.3. Recording and Follow-Up of AEs and/or SAEs****AE and SAE Recording**

- When an AE/SAE occurs, it is the responsibility of the investigator to review all documentation (for example, hospital progress notes, laboratory reports, and diagnostics reports) related to the event.
- The investigator will then record all relevant AE/SAE information in the CRF.
- It is **not** acceptable for the investigator to send photocopies of the participant's medical records to the sponsor or designee in lieu of completion of the AE/SAE CRF page.
- There may be instances when copies of medical records for certain cases are requested by the sponsor or designee. In this case, all participant identifiers, with the exception of the participant number, will be redacted on the copies of the medical records before submission to the sponsor or designee.
- The investigator will attempt to establish a diagnosis of the event based on signs, symptoms, and/or other clinical information. Whenever possible, the diagnosis (not the individual signs/symptoms) will be documented as the AE/SAE.

### Assessment of Intensity

The investigator will make an assessment of intensity for each AE and SAE reported during the study and assign it to 1 of the following categories:

- Mild: An event that is easily tolerated by the participant, causing minimal discomfort and not interfering with everyday activities.
- Moderate: An event that causes sufficient discomfort and interferes with normal everyday activities.
- Severe: An event that prevents normal everyday activities. An AE that is assessed as severe should not be confused with a SAE. Severe is a category utilized for rating the intensity of an event; and both AEs and SAEs can be assessed as severe.

An event is defined as ‘serious’ when it meets at least 1 of the predefined outcomes as described in the definition of an SAE, NOT when it is rated as severe.

### Assessment of Causality

- The investigator is obligated to assess the relationship between study intervention and each occurrence of each AE/SAE.
- A ‘reasonable possibility’ of a relationship conveys that there are facts, evidence, and/or arguments to suggest a causal relationship, rather than a relationship cannot be ruled out.
- The investigator will use clinical judgment to determine the relationship.
- Alternative causes, such as underlying disease(s), concomitant therapy, and other risk factors, as well as the temporal relationship of the event to study intervention administration will be considered and investigated.
- The investigator will also consult the Investigator’s Brochure (IB) and/or Product Information, for marketed products, in his/her assessment.
- For each AE/SAE, the investigator **must** document in the medical notes that he/she has reviewed the AE/SAE and has provided an assessment of causality.
- There may be situations in which an SAE has occurred and the investigator has minimal information to include in the initial report to the sponsor or designee. However, it is very important that the investigator always make an assessment of causality for every event before the initial transmission of the SAE data to the sponsor or designee.
- The investigator may change his/her opinion of causality in light of follow-up information and send an SAE follow-up report with the updated causality assessment.
- The causality assessment is one of the criteria used when determining regulatory reporting requirements.

**Follow-Up of AEs and SAEs**

- The investigator is obligated to perform or arrange for the conduct of supplemental measurements and/or evaluations as medically indicated or as requested by the sponsor or designee to elucidate the nature and/or causality of the AE or SAE as fully as possible. This may include additional laboratory tests or investigations, histopathological examinations, or consultation with other health care professionals.
- New or updated information will be recorded in the originally completed CRF.
- The investigator will submit any updated SAE data to the sponsor or designee within 24 hours of receipt of the information.

**10.3.4. Reporting of SAEs****SAE Reporting via an Electronic Data Collection Tool**

- The primary mechanism for reporting an SAE will be the electronic data collection tool.
- If the electronic system is unavailable, then the site will use the paper SAE data collection tool (see next section) in order to report the event within 24 hours.
- The site will enter the SAE data into the electronic system as soon as it becomes available.
- After the study is completed at a given site, the electronic data collection tool will be taken off-line to prevent the entry of new data or changes to existing data.
- If a site receives a report of a new SAE from a study participant or receives updated data on a previously reported SAE after the electronic data collection tool has been taken off-line, then the site can report this information on a paper SAE form (see next section) or to the medical monitor by telephone.
- Contacts for SAE reporting can be found in the site training documents.

**SAE Reporting via Paper CRF**

- Facsimile transmission of the SAE paper CRF is the preferred method to transmit this information to the sponsor or designee.
- Initial notification via telephone does not replace the need for the investigator to complete and sign the SAE CRF pages within the designated reporting time frames.
- Contacts for SAE reporting can be found in the site training documents.

## 10.4. Appendix 4: Contraceptive Guidance and Collection of Pregnancy Information

### Definitions:

#### Woman of Childbearing Potential

A woman is considered fertile following menarche and until becoming postmenopausal, unless permanently sterile (see below).

If fertility is unclear (for example, amenorrhea in adolescents or athletes) and a menstrual cycle cannot be confirmed before first dose of study intervention, additional evaluation should be considered.

Women in the following categories are not considered women of childbearing potential:

- premenarchal, and
- premenopausal female with 1 of the following:
  - documented hysterectomy
  - documented bilateral salpingectomy, or
  - documented bilateral oophorectomy.

For individuals with permanent infertility due to an alternate medical cause other than the above, (for example, mullerian agenesis, androgen insensitivity), investigator discretion should be applied to determining study entry.

Note: Documentation can come from the site personnel's review of the participant's medical records, medical examination, or medical history interview.

- Postmenopausal female is defined as, women with:
  - 12 months of amenorrhea for women  $>55$ , with no need for follicle-stimulating hormone (FSH)
  - 12 months of amenorrhea for women  $>40$  years old with FSH  $\geq 40$  mIU/mL and no other medical condition such as anorexia nervosa and not taking medications during the amenorrhea (for example, oral contraceptives, hormones, gonadotropin-releasing hormone, anti-estrogens, selective estrogen receptor modulators (SERMs), or chemotherapy that induced amenorrhea)

#### Contraception Guidance

Contraception is described in Section 5.1, Inclusion Criteria [7].

#### Collection of Pregnancy Information

##### Male participants with partners who become pregnant

- The investigator will attempt to collect pregnancy information on any male participant's female partner who becomes pregnant while the male participant is in this study. This applies only to male participants who receive lebrikizumab.

- After obtaining the necessary signed informed consent from the pregnant female partner directly, the investigator will record pregnancy information on the appropriate form and submit it to the sponsor within 24 hours of learning of the partner's pregnancy. The female partner will also be followed up to determine the outcome of the pregnancy. Information on the status of the mother and child will be forwarded to the sponsor. Generally, the follow-up will be no longer than 6 to 8 weeks following the estimated delivery date. Any termination of the pregnancy will be reported, including fetal status (presence or absence of anomalies) and indication for the procedure.

